## 11.2 Randomization Procedures

Randomization is defined as the process of assigning a participant to a study arm. Recruited and enrolled subjects will be block randomized in a 1:1:1:1:1 ratio into their assigned treatment group via a system developed and managed by the PATH designated CRO. Participants will be enrolled into the study and randomized using the Interactive Web Response System component of the Advantage eClinical database system. The system will assign subjects to study arms based on the randomization plan. Randomization will be stratified by site to achieve approximately half of the total subjects in each group from each site. Full details of the randomization procedures will be detailed in a randomization plan developed by the PATH designated CRO.

# 11.3 Sample Size

#### Immunogenicity:

It is anticipated that no more than 10% of subjects will be seropositive at baseline and that no less than 85% of subjects will be evaluable for the immunogenicity assessments.

The primary objective includes three non-inferiority comparisons of Cecolin® at 0 and 6 months, 0 and 12 months, or 0 and 24 months compared to Gardasil® at 0 and 6 months. To control the

type I error for the three co-primary non-inferiority hypotheses a Bonferroni correction resulting in a one-sided alpha of 0.0083 and corresponding to 98.3% confidence intervals (CI) will be used. To account for the simultaneous assessment of serotypes 16 and 18, 95% power is required for each comparison to achieve 90% power overall for the primary objective  $(0.95^2 \approx 0.90)$ .

Non-inferiority will be demonstrated if the lower bound of the 98.3% CI of the geometric mean concentration (GMC) ratio is greater than 0.5 for both HPV 16 and HPV 18. Assuming an IgG standard deviation of 0.65 of the log10 scale, adjustment for center, 10% baseline seropositive, and 15% dropout 205 subjects per arm will result in 90% power overall for the primary non-inferiority comparisons. The non-inferiority margin of 0.5 was selected in accordance with the WHO Technical Report Series #962. 

A sample size of 205 in the mixed schedule Gardasil® at 0 months and Cecolin® at 24 months provides 96% power for similar non-inferiority comparisons to Gardasil® at 0 and 6 months for both serotypes at the one-sided alpha 0.025 level. Similarly, the 24-month comparison of the 0,6 Gardasil® and 0,6 Cecolin® groups has greater than 90% power for non-inferiority comparisons for both serotypes at the one-sided alpha 0.025 level.

Analyses of the PBNA data will be descriptive in nature. However, the 20% sub-sample of subjects, resulting in approximately 20 subjects per arm per site or 200 overall for relevant timepoints, will provide a lower bound above 0.6 for the 95% CI for a Spearman's rank correlation of 0.7 or higher.

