Considerations	To control the type I error for the three co-primary non-inferiority hypotheses, a Bonferroni correction resulting in a one-sided alpha of 0.008 and corresponding 98.3% confidence intervals is used. Additional assumptions include 15% dropout, 10% baseline seropositivity, a 0.5 lower bound for non-inferiority of the GMC ratios, and an IgG standard deviation of 0.65 on the log base 10 scale. With these assumptions, 205 subjects per arm or 1025 subjects overall for the primary comparisons are required to achieve 95% for each serotype (16 and 18) or 90% power overall. The mixed 0,24 Gardasil® and Cecolin® will similarly have 205 subjects to provide the same precision for immunogenicity and safety estimates as the four primary arms.		

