# 2.2 Study Objectives

# 2.2.1 Co-Primary Objectives

• Demonstrate the non-inferiority of Cecolin® administered on 0, 6-month; 0, 12-month; and 0, 24-month two-dose regimens, to Gardasil® using a 0, 6-month two-dose regimen, based on HPV Immunoglobulin G (IgG) antibody levels measured one month after the last dose for HPV types 16 and 18

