# 11 STATISTICAL CONSIDERATIONS

## 11.1 Overview and General Design

This is a multi-center, randomized, active-controlled, open-label study which will enroll total of 1025 girls aged 9 to 14 years in two countries; Bangladesh and Ghana. Subjects will be block randomized 1:1:1:1:1 and stratified by site to receive Cecolin® at 0 and 6 months, 0 and 12 months, or 0 and 24 months, Gardasil® at 0 and 6 months, or Gardasil® at 0 months and Cecolin® at 24 months (see Figure 1). The primary objective is to demonstrate non-inferiority of the three Cecolin® arms to Gardasil® arm. Key secondary objectives are related to safety and tolerability, seroconversion, and immunogenicity of all five arms.

A formal statistical analysis plan (SAP) will be developed and finalized prior to interim analysis. The SAP will include additional statistical analysis detail (e.g., more detail of analysis populations, summary of statistical strategies).

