5. SAMPLE SIZE CONSIDERATIONS

Immunogenicity:

It is anticipated that no more than 10% of subjects will be seropositive at baseline and that no less than 85% of subjects will be evaluable for the immunogenicity assessments; see Section 6.3 for definitions of the immunogenicity analysis populations.

The primary objective includes three non-inferiority comparisons of Cecolin® at 0 and 6 months, 0 and 12 months, or 0 and 24 months compared to Gardasil® at 0 and 6 months. To control the type I error for the three co-primary non-inferiority hypotheses a Bonferroni correction resulting in a one-sided alpha of 0.0083 and corresponding to 98.3% confidence intervals (CI) will be used. To account for the simultaneous assessment of serotypes 16 and 18, 95% power is required for each comparison to achieve 90% power overall for the primary objective (0.952 \approx 0.90).

Non-inferiority will be demonstrated if the lower bound of the 98.3% CI of the geometric mean concentration (GMC) ratio is greater than 0.5 for both HPV 16 and HPV 18. Assuming an IgG standard deviation of 0.65 of the log10 scale, adjustment for center, 10% baseline seropositive (see Section 3.3), and 15% dropout 205 subjects per arm will result in 90% power overall for the primary non-inferiority comparisons. The non-inferiority margin of 0.5 was selected in accordance with the WHO Technical Report Series #962.

A sample size of 205 in the mixed schedule Gardasil® at 0 months and Cecolin® at 24 months provides 96% power for similar non-inferiority comparisons to Gardasil® at 0 and 6 months for both serotypes at the one-sided alpha 0.025 level. Similarly, the 24-month comparison of the 0,6 Gardasil® and 0,6 Cecolin® groups has greater than 90% power for non-inferiority comparisons for both serotypes at the one-sided alpha 0.025 level.

Analyses of the PBNA data will be descriptive in nature. However, the 20% sub-sample of subjects, resulting in approximately 200 overall for relevant timepoints, will provide a lower bound above 0.6 for the 95% CI for a Spearman's rank correlation of 0.7 or higher.

Safety:

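### The stated 90% power for the primary objective is the power for one Cecolin regimen; for all three regimens together it is about 78–86%

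*Protocol*

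**What the plan says.** Protocol 2.2.1 sets the co-primary objective: "Demonstrate the non-inferiority of Cecolin® administered on 0, 6-month; 0, 12-month; and 0, 24-month two-dose regimens", each against Gardasil at 0 and 6 months. Protocol 11.1 puts it more briefly: "The primary objective is to demonstrate non-inferiority of the three Cecolin® arms to Gardasil® arm". Protocol 11.3 and SAP 5 repeat that there are three comparisons and set a Bonferroni one-sided alpha of 0.0083 with 98.3% confidence intervals.

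The power statement follows directly. It begins "To account for the simultaneous assessment of serotypes 16 and 18" and goes on: "95% power is required for each comparison to achieve 90% power overall for the primary objective", with 0.95² ≈ 0.90 in brackets. SAP 5 then concludes that, after allowing for 10% baseline seropositivity and 15% dropout, "205 subjects per arm will result in 90% power overall for the primary non-inferiority comparisons"; Protocol 11.3 says the same. The Protocol Summary gives the target as "95% for each serotype (16 and 18) or 90% power overall".

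No section gives a power figure across the three regimens, and none states the true GMC ratio assumed.

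**The concern.** The same paragraph counts three regimens when it sets alpha and only one when it computes power. The exponent 2 stands for the two serotypes; the regimens do not enter it. If the 90% was meant per regimen, the label is wrong. If it was meant for the objective as written, the number is wrong.

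A sponsor, ethics committee or reader will take the figure as the chance of meeting the three-schedule objective. If one schedule later misses, the result would be judged against a stated prior chance of 10% when the design's own inputs imply a larger one. What is at stake is the interpretation of the design, not the validity of the tests.

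**Working it through.** **Inputs from Protocol 11.3 and SAP 5.** SD 0.65 on log10; margin 0.5, so the distance from a ratio of 1 is log10(2) = 0.30103; one-sided alpha 0.025/3 = 0.0083 (z = 2.394); 205 per arm. Losses of 15% and 10% leave 205 × 0.75 = 153.75 evaluable if added, or 205 × 0.85 × 0.90 = 156.8 if multiplied.

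**Assumed, because not stated.** The same true GMC ratio for every regimen and serotype, 1 unless noted; between-serotype correlation ρ from 0 to 0.9, with 1 as the limit.

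**Step 1: reproduce the plan's figure.** SE = 0.65 × √(2/n); power ≈ Φ(0.30103/SE − 2.394).
- n = 153.75: SE = 0.0741, 4.061 − 2.394 = 1.667, power 95.2% (95.0% by noncentral t).
- n = 156.8: SE = 0.0734, 4.101 − 2.394 = 1.707, power 95.6% (95.4% by noncentral t).
- One regimen, both serotypes, independent: 0.9503² = 90.3% and 0.9543² = 91.1%.

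The stated 95% and 90% therefore reproduce at a true ratio of 1, for one regimen.

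**Step 2: which evaluable number.** The text also says "no less than 85% of subjects will be evaluable for the immunogenicity assessments", which could be read as 205 × 0.85 = 174.25 per arm after all losses. Two things speak against that reading:
- The 154 evaluable needed for 95% per serotype would require only about 181 enrolled (154/0.85).
- For the mixed arm the plan says 205 "provides 96% power for similar non-inferiority comparisons to Gardasil® at 0 and 6 months for both serotypes" at one-sided 0.025. The calculation gives 96.4% at 153.75, 96.7% at 156.8 and 98.1% at 174.25.

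The plan's own figures fit 154–157.

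**Step 3: all three regimens on both serotypes.** The regimens share the Gardasil arm, so with equal arms two regimen comparisons have correlation (σ²/n)/(2σ²/n) = 0.5. Ignoring this would give 0.95⁶ = 73.5%, which is too low. Four arms by two serotypes were simulated with 400,000–600,000 replicates and t critical values. The ranges below cover pairwise and four-arm pooled variance.

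| Power, all three regimens (%) | ρ = 0 | ρ = 0.5 | ρ = 0.9 | ρ = 1 |
|---|---|---|---|---|
| Exactly 95% per comparison | 77.7–78.1 | 80.1–80.5 | 84.1–84.6 | 88.1–88.4 |
| Ratio 1, n = 153.75 | 77.8–78.3 | 80.1–80.6 | 84.2–84.6 | 88.3–88.5 |
| Ratio 1, n = 156.8 | 79.3–79.7 | 81.5–81.8 | 85.4–85.8 | 89.1–89.3 |
| Ratio 1, n = 174.25 | 86.5–86.8 | 87.8–88.1 | 90.4–90.6 | 93.0–93.2 |

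Hand check: at ρ = 1 the two serotypes act as one, and at ρ = 0 they are independent, so the ρ = 0 value should be the square of the ρ = 1 value. At n = 153.75, 0.883² = 78.0% and 0.885² = 78.3%, as tabulated. The normal approximation changes these results by less than about 1 point.

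In the first row, which uses the plan's required 95% per comparison, no correlation reaches 90%. One regimen on both serotypes has 90–94% at 154–157 evaluable and ratio 1.

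**Step 4: sensitivity to the true ratio (154–157 evaluable, ρ 0 to 0.9), all three regimens.**
- 0.90: 48–63%
- 0.95: 65–76%
- 1.05: 87–92%
- 1.1: 93–95%
- 1.0 for the 0, 6 schedule with 1.2 for the two longer ones: 89–93%

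For 90% on all three at equal ratios, each comparison would need 98.0, 97.8, 97.1 or 95.9% power at ρ = 0, 0.5, 0.9 or 1.

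**The case against.** The strongest reply is that the text shows what it means. The sentence opens with the two serotypes and prints the square, and the Protocol Summary likewise moves from each serotype to the overall figure. The design also points to a separate claim per regimen: alpha is split, an interval is computed for each comparison, and the Month 7 interim analyses groups 1 and 4 alone. Nothing makes the trial's success depend on all three. On that reading 90% per regimen is a proper target, and power is about 99% for at least one regimen and 94–97% for at least two.

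Much of this stands. The sample size is right for one regimen, and Bonferroni is coherent with separate claims. But no sentence says that each regimen is a separate claim, and calling the result overall power for an objective defined as three comparisons does not say per regimen. Nor does 90% fit an at-least-one reading, where the figure would be about 99%.

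The reply is also right that the all-three figure depends on inputs the documents do not give. Ratios somewhat above 1 can bring it to 90% or more, and ratios below 1 lower it well under 78%. The range should therefore appear with its assumptions, and the sponsor should confirm the ratio it used.

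**Conclusion.** The concern holds, as a minor misstatement of power. The 90% belongs to each regimen on both serotypes. For the objective as written, the figure is about 78–86%, so the chance that at least one regimen misses is about 14–22%. This rests on a true ratio of 1 throughout, 154–157 evaluable per arm, the plan's SD, margin and alpha, a shared control, and an assumed between-serotype correlation of 0 to 0.9.

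A related drafting gap is that the both-serotype condition appears in Protocol 11.3 and SAP 5 but is not repeated in the pass rules of Protocol 11.5.1.1.1 and SAP 8.1.

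**What to change.** 1. In the Protocol Summary (Statistical Considerations), Protocol 11.3 and SAP 5, state that 205 per arm gives 90% power for each regimen on both serotypes at the assumed true GMC ratio. That ratio appears to be 1; the sponsor should confirm it. Add that the probability of all three regimens succeeding is about 78–86%, for an assumed between-serotype correlation of 0 to 0.9 and 154–157 evaluable per arm.
2. In Protocol 11.3 and 11.5.1 and SAP 6.8 and 8.1, add one sentence: each regimen is a separate claim at one-sided 0.0083 (98.3% CI), met only if both HPV 16 and HPV 18 pass.
3. Keep the Bonferroni split and the sample size. If the sponsor nevertheless wanted another alpha rule, it would have to be fixed before the Month 7 results are known and changed wherever the 98.3% rule appears.

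The cost is text only, with no change to N, analyses, tables or figures. Under Protocol 13.1 protocol edits need prior written approval from all IECs/IRBs, so they fit best in the next planned amendment; the SAP can be corrected separately. The one drawback is a less favourable stated power for the full three-regimen objective.

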#### Safety:

There is greater than 90% power to observe a severe or serious AE at a rate of  $\geq 0.4\%$  among the 615 subjects that will receive Cecolin® in month 0 and a rate of  $\geq 0.6\%$  among the 410 receiving at least one dose of Gardasil®. Within any arm there is a greater than 90% probability of observing at least one severe or serious AE with a  $\geq 1.2\%$ . The upper bounds of the 95% CIs implied if no AEs are observed are show in Table 2.

Table 2: Detectable rates of AEs and 95% CI upper bounds if no events are observed.

Sample size		Upper bound of 95% confidence interval if no events are observed
615	0.4%	0.6%
410	0.6%	0.9%
205	1.2%	1.8%

## 11.4 Definitions of Populations to be Analyzed

## 11.4.1 Enrolled Population

All screened participants who provide informed consent and are randomized regardless of the participant's treatment status in the trial.

## 11.4.2 Total Vaccinated Population

All participants in the enrolled population who were randomized and received at least one dose of study vaccination. All safety analyses will be performed using this population. Treatment groups for safety analysis will be assigned according to the actual treatment received at Day 1.

## 11.4.3 Per Protocol population

All participants in the total vaccinated population with no major protocol deviations that are determined to potentially interfere with the immunogenicity assessment of the study vaccine, were seronegative for the relevant HPV type at baseline, and have a valid serology result for the relevant time point. This population will serve as the primary analysis population for the immunogenicity endpoints. The population will be adapted by time point to include all eligible subjects' data up to the time of the disqualifying protocol deviation.

The criteria for exclusion of participants from the Per Protocol Population will be based on the review of protocol deviations at a Data Review Meeting (DRM) attended by the sponsor, investigator, and CRO representatives.

## 11.5 Analytical Methodology

All analyses will be performed by the PATH designated CRO, under the supervision and responsibility of the sponsor. All statistical methods shall be detailed in a Statistical Analysis Plan (SAP) that will be finalized prior to the interim analysis.

SAS version 9.4 or greater will be used for analysis. Except where otherwise indicated in this document or the SAP, summary statistics will be composed of the mean, standard deviation, 1st, 2nd, and 3rd quartile, and the minimum and maximum for continuous variables. For categorical variables, the count and proportion (using one digit beyond the decimal point) will be presented. All study data will be presented in listings. In general, summary tables will be presented by group, including a column for the total across all participants.

For all immunological assays with predefined limits of quantitation, percentiles, and bootstrapbased confidence intervals (CIs) which achieve the LLOQ or ULOQ will be replaced with "<LLOQ" or ">ULOQ", as appropriate. Analysis of immunological assays may be supplemented by reverse cumulative distribution (RCD) curves with each group for a given time point displayed on the same plot, and different panels (preferred) or figures for different time points.

Baseline characteristics, including age, height and weight will be summarized for both the total vaccinated and per protocol populations. Baseline characteristic summaries will be supplemented with two-sided level  $\alpha = 0.05$  statistical assessment of differences between groups, using Fisher's exact test for categorical variables, and the Kruskal-Wallis test for continuous variables. For the total vaccinated population, medical history will be listed and summarized by category. Prior and concomitant medications will be coded according to WHO Drug version 2018, listed, and summarized by Anatomic Therapeutic Chemical classification level 1 and level 4 within level 1, where each subject only contributes once per drug category. Summaries of participant disposition will be prepared for all subjects, including the number and percent screened, enrolled, and within each study population, as well as a CONSORT diagram describing study participation and dropout. The reasons not enrolled will be summarized, along with the withdrawal rate and the reasons for

withdrawal, as well as listed. A summary and listing of visit attendance will be prepared, in addition to a summary and listing of vaccine administration, and a sample collection/availability for each sample type.

# 11.5.1 Analysis of primary objective/s

## 11.5.1.1 Immunogenicity

The primary immunogenicity assessments will take place within the per protocol population. Supplementary analyses will be conducted in the total vaccinated cohort. GMC/T, GMC/T ratio, and corresponding confidence limits, will be calculated using SAS LSMEANS of the log-scale coefficients which will be back-transformed in order to compute the estimate and corresponding confidence limits for the relevant quantity. The GMT ratio and corresponding two-sided 98.3% CI for each comparison will be computed separately for each comparison to Gardasil® 0,6. All analyses will include adjustment for trial center. Sensitivity analyses may be considered for application in the total vaccinated cohort utilizing SAS PROC LIFEREG, incorporating censoring where appropriate at LLOQ and ULOQ, and a Normal error distribution on the log scale, and adjustment for baseline concertation or titer on the log scale.

## 11.5.1.1.1 Anti-HPV 16 and 18 IgG

Anti-HPV 16 and 18 IgG antibody GMCs, measured by ELISA at baseline and one month after the second dose on Month 7 (for the 0, 6-month arms), Month 13 (for the 0, 12-month arm) or Month 25 (for the 0, 24-month arm) for the two-dose Cecolin® and Gardasil® arms will be summarize using assay-specific LLOQ/ULOQ as appropriate by arm and by trial center.

Serotype-specific GMCs will be summarized by arm as a continuous variable and corresponding 95% CIs will be provided. These results will be supplemented with a CI for the median, computed via the percentile bootstrap method, using n=10,000 replicates.

The GMC ratios and corresponding two-sided 98.3% CI for each comparison of a Cecolin® arm to the Gardasil® 0-6 arm will be computed. If the lower bound of the 98.3% CI is >0.5, non-inferiority will have been demonstrated.

## 11.5.2 Analysis of secondary objective/s

#### 11.5.2.1 Immunogenicity

The analysis of secondary objectives will utilize the same study populations and analytic methods. However, 95% confidence intervals will be used for secondary objectives unless otherwise stated.

# 11.5.2.1.1 Anti-HPV 16 and 18 lgG

Anti-HPV 16 and 18 IgG antibody GMCs, measured by ELISA at baseline and one month after the second dose on Month 7 (for the 0, 6-month arms), Month 13 (for the 0, 12-month arm) or Month 25 (for the 0, 24-month arm) for the two-dose Cecolin® and Gardasil® arms as well as the mixed regimen arm, will be summarize using assay-specific LLOQ/ULOQ as appropriate by arm and by trial center.

For each time point, serotype-specific GMCs will be summarized by arm as a continuous variable and corresponding 95% CIs will be provided. These results will be supplemented with a CI for the median, computed via the percentile bootstrap method, using n=10,000 replicates.

The GMC ratio and corresponding two-sided 95% CI for the comparison of a Cecolin® arms and mixed dose arm to the Gardasil® 0,6 arm will be computed.

Similarly, the GMC ratio and corresponding two-sided 95% CI for the 0,6 Cecolin® arm and 0,6 Gardasil ® arm and 24-months after the first dose will be computed.

Seroconversion rate, defined as a 4-fold rise in anti-HPV 16 and 18 IgG antibody as measured by ELISA at baseline and one month following the last dose will be summarized as a categorical variable. The type-specific difference in response proportion between the Cecolin® and mixed arms compared to the Gardasil® arm 1 month after the second dose will be computed with a corresponding 95% CI computed via the Miettinen and Nurminen score method.

# 11.5.2.1.2 Anti-HPV 16 and 18 serum neutralizing antibody titers

Anti-HPV 16 and 18 serum neutralizing antibody GMTs measured by PBNA on a representative subset (20%) of samples at all time points will be summarized using assay-specific LLOQ/ULOQ as appropriate by arm and by trial center.

For each time point, serotype-specific GMTs will be summarized by arm as a continuous variable and corresponding 95% CIs will be provided. These results will be supplemented with a CI for the median, computed via the percentile bootstrap method, using n=10,000 replicates.

Correlation between neutralizing antibody titers measured by PBNA and IgG antibody concentrations measured by ELISA will be summarized on the continuous scale and seroconversion agreement will be summarized.

